3.1.4 Open-label treatment epoch (Epoch 4)

All patients who were re-randomized to placebo on Day 113 but completed the randomized withdrawal epoch (Epoch 3) without re-flare will enter Epoch 4. They will present for scheduled visits but will not receive any investigational drug. In case they re-flare, they will enter the open-label treatment arm receiving canakinumab 150 mg (or 2 mg/kg for patients weighing ≤ 40 kg) q8w. In case of experiencing a flare, up-titration will be allowed as specified in Section 3.1.3.2.

All other patients will enter the long-term safety open-label treatment epoch of 72 weeks duration. They will continue on their last dosing regimen as administered during the randomized withdrawal epoch (Epoch 3). Visits to assess efficacy and safety are scheduled at 8 weeks intervals during the open-label treatment epoch (Epoch 4).

In case of re-flares (PGA ≥ 2 and CRP ≥ 30 mg/L) before the next scheduled visit, (step-wise) up-titration up to a dosing regimen of canakinumab 300 mg (or 4 mg/kg for patients weighing ≤ 40 kg) q4w will be allowed. The same principles for up-titration as outlined in [Section 3.1.2.3](#) or [Section 3.1.3.2](#) will apply.

No down-titration will be allowed during Epoch 4.

Visits to assess efficacy and safety are scheduled at 8 weeks intervals during the open-label treatment epoch (Epoch 4). Patients might receive an up-titration if they re-flare during Epoch 4. Patients up-titrated to q4w administration will come back every 4 weeks for unscheduled visits at Day 309, Day 365, Day 421, Day 477, Day 533, Day 589, Day 645, Day 701 and Day 757 in addition to the visits scheduled defined in Table 6-2.

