8.5.2 Malignancy Adjudication Committee

An external, independent Malignancy Adjudication Committee (MAC) has been formed on a program level and will review pertinent data from this trial.

The mission of the MAC is to independently and blindly review, evaluate and categorize reports of malignancy events across all potential indications and therapeutic areas in the canakinumab development program.

The members, detailed mission and procedures of the MAC are detailed in the MAC Charter which is available upon request.

9 Data analysis

All data will be analyzed separately for each independent cohort (TRAPS, HIDS, crFMF).

Randomized treatment epoch (Epoch 2):

Treatment arms for the primary efficacy analyses will include canakinumab 150 mg sc q4w and placebo.

For some efficacy endpoints and specific safety endpoints (like AEs or laboratory abnormalities), treatment arms will include

- canakinumab 150 mg q4w
- placebo
- canakinumab 150 mg – canakinumab 300 mg q4w
- placebo – canakinumab 150 mg q4w

In addition, patients in the canakinumab arm (150 mg q4w) flaring after Week 4 or placebo patients flaring after Week 4 or placebo patients flaring after receiving the first escape treatment will enter open-label escape and receive up to a maximum of 300 mg (or 4 mg/ kg) q4w until the end of study. Only descriptive safety data will be presented after patients enter open-label escape.

Randomized withdrawal epoch (Epoch 3):

Treatment arms for the safety and efficacy analyses will include, for canakinumab responders at the end of the epoch 2:

- canakinumab 150 mg q8w
- placebo.

And the two open-label treatment arms:

- canakinumab 150 mg q8w
- canakinumab 300 mg q8w

Open-label treatment epoch (Epoch 4):

Treatment arms for the safety and efficacy analyses will include (taken into account their regimen in Epoch 3):

- placebo - canakinumab 150 mg q8w
- placebo- canakinumab 150 mg q4w
- canakinumab 150 mg q8w - canakinumab 150 mg q8w
- canakinumab 150 mg q8w - canakinumab 150 mg q4w
- canakinumab 150 mg q8w
- canakinumab 300 mg q8w
- canakinumab 300 mg q8w – canakinumab 300 mg q4w

Safety data for the subgroup of patients coming from ACZ885D2203 and/or the subsequent Multiple Patient Program (MPP) treatment plan CACZ885D2207M collected in Epoch 3 and 4 will separately be reported from the other patients who will be screened and randomized in Epoch 2.

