1.3 Treatment group definitions

The following study epoch will be considered for analysis:

- **Epoch 2:** A randomized treatment epoch of 16 weeks. This randomized treatment epoch will include 2 possible escape options: Blinded escape, Open-label treatment
- **Epoch 3:** A randomized withdrawal epoch of 24 weeks

- **Epoch 4:** An open-label treatment epoch of 72 weeks.

Treatment groups for analysis will include:

Randomized treatment epoch (Epoch 2):

Treatment arms for the primary and secondary efficacy analyses will only include canakinumab 150 mg sc q4w and placebo.

Other efficacy and safety data will be displayed in Epoch 2 in the following way:

- Patients being randomized and not having a flare in epoch 2 (and not having received add-on dose or any up-titration)
- Patients being randomized and having at least one flare in epoch 2 and having been up-titrated only once (or received add-on dose) (150mg q4->300mg q4; Placebo->150mg q4)
- Patients being randomized and having at least one flare in epoch 2 and having been up-titrated at least twice (Placebo->300mg q4)

----- No flare ----- ----- >= 1 Flare -----

Randomized	Open –label arm			
150mg q4	Placebo	150mg q4->300mg q4	Pla->150mg q4	Pla->150mg q4->300mg q4

Randomized withdrawal epoch (Epoch 3):

As one of the objectives in epoch 3 is to look at the maintenance of efficacy, patients will be categorized in two groups: those being randomized and keeping their initial treatment arm until the end of epoch 3 (i.e. no having a flare) and the other patients where the cumulative dose (in mg) over the 24 weeks will be analyzed.

Safety and efficacy data will be displayed in Epoch 3 in the following way:

- Re-randomized & no up-titration	----	Cumulative dose in mg over 24 weeks	----	
150mg q8	Placebo	<600mg	600mg - <1200mg	≥1200mg

[figure not shown]
The cut-offs of 600mg, 1200mg were decided based on all options for cumulative dose over 24 weeks depending on the number of flares and initial dose regimen at start of epoch 3.

Example on how the cumulative dose is calculated over the 24 weeks:

Considering a patient taking initially 150 mg q8w at start of epoch 3 and having only one flare in epoch 3 then the patient will up titrate to 150 mg q4w. Here are the different cases. The first line shows the initial schedule with no flare. If no flare, the patient receives 3 injections of 150 mg each so a total of 450 mg over 24 weeks, from Day 113 to Day 281, with no dose at day 281 (belongs to epoch 4).

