	Day 113	Day 141	Day 169	Day 197	Day 225	Day 253	Cumulative dose in mg
Dose: 150mg q8 with no flare	X 150mg		X 150mg		X 150mg		450mg
1 flare between D225- D253	X 150mg		X 150mg		X 150mg	X 150mg	600mg
1 flare between D197- D225	X 150mg		X 150mg		X 150mg	X 150mg	600mg
1 flare between D169- D197	X 150mg		X 150mg	X 150mg	X 150mg	X 150mg	750mg
1 flare between D141- D169	X 150mg		X 150mg	X 150mg	X 150mg	X 150mg	750mg
1 flare between D113- D141	X 150mg	X 150mg	X 150mg	X 150mg	X 150mg	X 150mg	900mg

Therefore for a patient taking initially 150mg q8w at the start of epoch 3 and having one flare in epoch 3, the range of cumulative dose over 24 weeks will be [600 mg-900 mg].

Notes: 1. Earlier the flare occurs, higher the cumulative dose is
2. More flares => increase of cumulative dose, but stable after 5 flares

Cumulative dose calculation for epoch 3:

For Patients weighing ≥ 7.5 kg and ≤ 40 kg, the dose is derived in mg/kg ie. Actual total dose (ml) $\times 150$ mg / Weight(kg) at visit.

- If the sum of the dose (mg/kg) in Epoch 3 is ≤ 7 mg/kg then the patient will be assigned to the dose level category <600 mg.
- If the sum of the dose (mg/kg) in Epoch 3 is >7 mg/kg - ≤ 15 mg/kg then the patient will be assigned to the dose level category ≥ 600 mg- <1200 mg.
- If the sum of the dose (mg/kg) in Epoch 3 is >15 mg/kg then the patient will be assigned to the dose level category ≥ 1200 mg.

For Patients weighing <7.5 kg, the dose is derived in mg/kg ie. Actual total dose (ml) $\times 75$ mg / Weight(kg) at visit.

[figure not shown]
- If the sum of the dose (mg/kg) in Epoch 3 is ≤ 7 mg/kg then the patient will be assigned to the dose level category <600 mg.
- If the sum of the dose (mg/kg) in Epoch 3 is >7 mg/kg - ≤ 15 mg/kg then the patient will be assigned to the dose level category ≥ 600 mg- <1200 mg.
- If the sum of the dose (mg/kg) in Epoch 3 is >15 mg/kg then the patient will be assigned to the dose level category ≥ 1200 mg.

Open-label treatment epoch (Epoch 4):

As few patients are expected having no flare in epoch 4 for 72 weeks, then safety and efficacy data will be displayed using the cumulative dose over the 72 weeks in Epoch 4 in the following way:

----- Cumulative dose in mg over 72 weeks -----
<2700mg $\geq 2700\text{mg} - < 5400\text{mg}$ $\geq 5400\text{ mg}$

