The cut-offs of 2700mg, and 5400mg were decided based on all options for cumulative dose over 72 weeks depending on the number of flares and initial dose regimen at start of epoch 4. The first group could be considered as patients taking initially 150mg q8w at start of epoch 4 with or without flare over 72 weeks, the second one grouping patients taking initially 150mg q4w or 300mg q8w at start of epoch 4 with or without flare over 72 weeks and the last one patients taking initially 300mg q4 with or without flare over 72 weeks.

Roll-over patients from ACZ885D2203/ CACZ885D2207M and naïve Japanese crFMF patients with non-exon 10 mutations and patients >28 days but <2 years old

Data for the subgroup of patients coming from ACZ885D2203 and/or the subsequent Multiple Patient Program (MPP) treatment plan CACZ885D2207M collected in Epoch 3 as well as canakinumab naïve Japanese crFMF patients with non-exon 10 mutations and patients >28 days but <2 years old collected in Epoch 2 and Epoch 3, will separately be reported from the other patients who will be screened and randomized in Epoch 2. For subgroup 1: Roll-over patients from ACZ885D2203/ CACZ885D2207M:

In epoch 3, for this subgroup of patients safety and efficacy data will be tabulated as follows:

----- Cumulative dose in mg over 24 weeks -----
<600mg 600mg - <1200mg $\geq 1200\text{mg}$

In epoch 4, this subgroup of patients will be reported together with the other patients as follows:

----- Cumulative dose in mg over 72 weeks -----

<2700mg \geq 2700mg- <5400mg \geq 5400 mg

For subgroup 2: Naïve Japanese crFMF patients with non-exon 10 mutations and patients >28 days but <2 years old:

Patient Demographics & other baseline characteristics and Adverse events data for this subgroup will be tabulated under one treatment group ACZ885. All other safety and efficacy data will be listed under one treatment group ACZ885 in epoch 2 and epoch 3. This subgroup of patients will also be reported together with the other patients in epoch 4 using same cumulative dose categories.

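### In Epoch 4 the cumulative-mg columns match the regimens they are said to represent only for full-course patients; in Epoch 3 the same mixing of dose with time on drug is partial

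*SAP*

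**What the plan says.** **Epoch 3.** SAP 1.3 shows re-randomized patients without up-titration by arm. The second group is "the other patients where the cumulative dose (in mg) over the 24 weeks will be analyzed", in columns of <600, 600 to <1200 and ≥1200 mg. On the cut-offs it says: "The cut-offs of 600mg, 1200mg were decided based on all options for cumulative dose over 24 weeks". A worked example follows for a patient who starts on 150 mg q8w.

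**Epoch 4.** SAP 1.3 says "safety and efficacy data will be displayed using the cumulative dose over the 72 weeks in Epoch 4", in columns of <2700, 2700 to <5400 and ≥5400 mg. The first column is explained as 150 mg q8w starters, the second as 150 mg q4w or 300 mg q8w starters, and "the last one patients taking initially 300mg q4 with or without flare over 72 weeks".

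No rule scales the total for time on treatment or says where a patient who stops early belongs.

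**Protocol.** Section 9 groups Epoch 4 by regimen: "Treatment arms for the safety and efficacy analyses will include (taken into account their regimen in Epoch 3". Section 3.1.4 adds a drug-free group, the patients re-randomized to placebo who did not re-flare in Epoch 3: "They will present for scheduled visits but will not receive any investigational drug".

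**The concern.** Total mg is dose level multiplied by time on drug, so a patient's column is known only at the end of the epoch. If stopping treatment lowers the column, an event that makes a high-dose patient stop is tabulated under a lower dose.

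Stopping is tied to safety here. Protocol 5.5.9 requires discontinuation for malignancy, confirmed tuberculosis, serious infection with neutropenia and certain laboratory findings, and keeps those patients in the study. The SAP 1.3 groups are used for adverse events of special interest, including adjudicated infections and malignancies (SAP 1.13.1), and for disposition (1.6), laboratory data (1.13.3), vital signs (1.13.4) and the exploratory efficacy displays (1.10.5). Long-term safety is a secondary objective and the stated purpose of Epoch 4. A reader of these tables looks for a relation between dose and harm, and this grouping can blur it.

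**Working it through.** **1. Reproduce the SAP example (Epoch 3).** There are six q4w dosing days: 113, 141, 169, 197, 225 and 253, "with no dose at day 281 (belongs to epoch 4"). A q8w patient uses three of them; after a flare every later day is dosed.

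- No flare: 3 × 150 = 450 mg.
- Flare between Days 113 and 141: 6 × 150 = 900 mg.
- Flare between Days 141 and 197: 5 × 150 = 750 mg.
- Flare between Days 197 and 253: 4 × 150 = 600 mg.

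This agrees with the SAP: "the range of cumulative dose over 24 weeks will be [600 mg-900 mg"].

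**2. Epoch 4, full courses.** Scheduled visits are eight weeks apart, and Protocol 3.1.4 adds nine q4w visits from Day 309 to Day 757. The q4w dosing days run from 281 to 757: (757 − 281)/28 + 1 = 18. A q8w patient has 9. I assume that no dose at Day 785 counts in Epoch 4.

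| Regimen, not escalated | Full course (mg) | Column | One dose fewer (mg) | Column |
|---|---|---|---|---|
| 150 mg q8w | 9 × 150 = 1350 | <2700 | 1200 | <2700 |
| 150 mg q4w | 18 × 150 = 2700 | 2700 to <5400 | 2550 | <2700 |
| 300 mg q8w | 9 × 300 = 2700 | 2700 to <5400 | 2400 | <2700 |
| 300 mg q4w | 18 × 300 = 5400 | ≥5400 | 5100 | 2700 to <5400 |

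Three of the four full courses equal a cut-off exactly. For 300 mg q4w, 8 doses (Day 477) give 2400 mg, the lowest column, and 9 to 17 doses give 2700 to 5100 mg, the middle column. Escalation does not loosen the top column: a 150 mg q4w starter who moves to 300 mg q4w from Day 309 reaches 150 + 17 × 300 = 5250 mg. Only 18 doses of 300 mg qualify.

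**3. Epoch 3, 300 mg.** The top column needs 1200/300 = 4 doses, out of at most 6.

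| Doses of 300 mg | Total (mg) | Column |
|---|---|---|
| 1 | 300 | <600 |
| 2 or 3 | 600 or 900 | 600 to <1200 |
| 4, 5 or 6 | 1200, 1500 or 1800 | ≥1200 |

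The mg/kg rule for patients up to 40 kg gives the same result: 4 mg/kg is ≤7; 8 and 12 lie above 7 and up to 15; 16 is >15.

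Flare also sets the column. A full-course 300 mg q8w starter has 900 mg without a flare, but 1200 to 1800 mg after a flare before Day 253. Timing matters for patients who stop: after the Day 225 dose, a flare before Day 197 has led to at least 1200 mg (top column), while a flare between Days 197 and 225 has led to 900 mg (middle).

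**4. If Day 785 were dosed in Epoch 4.** 300 mg q4w would total 19 × 300 = 5700 mg. One missed dose would leave 5400 mg, still in the top column; two would leave 5100 mg and lower it. Likewise 19 × 150 = 2850 mg and 10 × 300 = 3000 mg tolerate one missed dose (2700 mg each) but not two.

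**5. Illustration only.** The documents give no rates for stopping or missed doses. If 300 mg q4w stops were spread evenly over the 17 points before the last dose, 8/17 = 47% would fall in the lowest column and 9/17 = 53% in the middle. Earlier or later stopping moves this split anywhere from all lowest to all middle. With an independent chance of missing each dose of 0.5%, 1% or 2%, the share of 300 mg q4w completers leaving the top column is 1 − 0.995^18 = 9%, 1 − 0.99^18 = 17% or 1 − 0.98^18 = 31%.

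**The case against.** A reader might infer that anyone who stops early drops a column and that the top column can never contain a discontinuer, in both epochs. The documents do not support that.

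- In Epoch 3, four of six 300 mg doses reach the top column, so a patient who flared early can stop with two doses still due and remain there.
- Patients in the lowest column cannot drop, and some others keep their column. In Epoch 3, 300 mg q8w stopped after two of three doses (600 mg) sits with the full 900 mg. In Epoch 4, up-titrated patients may have mg to spare.
- Re-randomized patients without up-titration are shown by arm.
- In Epoch 4, a patient who withdraws after the Day 757 dose and before Day 785 keeps 5400 mg.

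All of this stands and limits the point.

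It can also be said that the SAP offers its regimen labels as a gloss, expects few patients without a flare in Epoch 4, and that Protocol 6.3 expects full compliance with site-given injections. The first two weaken the case for 150 mg q4w and 300 mg q8w, since escalation adds mg. They do not help 300 mg q4w, which has no further step. Full compliance does not prevent discontinuation.

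The mitigations are real. H5 compares re-randomized arms and counts discontinuers as non-responders (SAP 1.10.2.1). Exposure-adjusted AE rates use actual dose, and deaths, serious events and events leading to discontinuation are listed (SAP 1.13.1). But those rates are specified only by system organ class and preferred term, with no counterpart for laboratory, vital-sign, disposition or efficacy tables.

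Drug-free patients are a minor matter: the Epoch 4 Safety Set requires treatment in that epoch, so at 0 mg they could appear only in other tables.

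**Conclusion.** The point holds for Epoch 4 and in part for Epoch 3. In Epoch 4 a 300 mg q4w patient who stops before the last dose, or misses one, is shown one or two columns lower, and an adverse event that causes such a stop is shown there too. Un-escalated 150 mg q4w and 300 mg q8w patients drop one column on the same terms. In Epoch 3 only stops before the fourth 300 mg dose keep a patient out of the top column, and flare timing also moves patients between columns.

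The conclusion rests on 18 Epoch 4 dosing days with none at Day 785. The body of Protocol Table 6-2 is not available, but the Day 281 rule, the 72-week length and the match to the cut-offs all point that way. With a Day 785 dose, two missed doses rather than one would be needed. The Epoch 4 figures are for fixed-dose patients, because the SAP's mg/kg conversion is headed for Epoch 3 only.

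The effect is confined to descriptive safety and efficacy tables; H1 to H5 are unaffected. It is also tempting to say that a dose relation would be reversed. The arithmetic shows that events can be misplaced, but nothing in the documents shows a reversal. The change should be made because these tables carry the long-term safety objective.

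**What to change.** In SAP 1.3, make the main Epoch 3 open-label tables and the Epoch 4 tables by regimen at the start of the epoch, with a separate no-drug group wherever drug-free patients are tabulated. This returns to the regimen basis of Protocol Section 9 but should not copy its Epoch 4 sequence columns: up-titration is itself a post-baseline event, and a patient who stops early has less time to be up-titrated.

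Present adverse events, serious adverse events, events of special interest and events leading to discontinuation by the regimen at onset, with person-time denominators. Keep cumulative mg only as an exposure summary. State where a re-randomized patient who stops without a flare is shown in Epoch 3; the SAP text (keeping the arm to the end of the epoch) and the column head (no up-titration) leave this open.

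The cost is SAP wording, reprogramming and some small columns in cohorts of about 60 randomized patients. No new data are needed.

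### Epoch 4 tables group patients by raw cumulative mg with no mg/kg conversion, so patients of 40 kg or less on the higher weight-based regimens mostly land in the group described as 150 mg q8w

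*SAP*

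**What the plan says.** SAP 1.3 (Treatment group definitions) states that "safety and efficacy data will be displayed using the cumulative dose over the 72 weeks in Epoch 4", in three groups of total mg received: <2700, 2700 to <5400 and ≥5400. It explains that "The cut-offs of 2700mg, and 5400mg were decided based on all options for cumulative dose over 72 weeks", taking account of flares and of the regimen at the start of the epoch. It then describes the groups loosely: "The first group could be considered as patients taking initially 150mg q8w at start of epoch 4", whether or not they flare. The middle group stands for starters on 150 mg q4w or 300 mg q8w, and the top group for starters on 300 mg q4w.

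Dosing is weight-based at low weight. Under Protocol 3.1.2.1 and 3.1.4, patients of 40 kg or less receive 2 mg/kg in place of 150 mg and 4 mg/kg in place of 300 mg.

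For Epoch 3 the SAP allows for this. Under "Cumulative dose calculation for epoch 3" it converts the dose of these patients to mg/kg. Sums of ≤7, >7 to ≤15 and >15 mg/kg go to the <600, 600 to <1200 and ≥1200 mg groups. Each of these rules names Epoch 3. No counterpart is given for Epoch 4. For the set that includes patients under 2 years, SAP 1.3 adds: "This subgroup of patients will also be reported together with the other patients in epoch 4 using same cumulative dose categories".

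**The concern.** Cut-offs built from 150 mg and 300 mg doses are applied to totals that, at 40 kg or less, depend on body weight as well as on regimen. A small child on the most intensive regimen can therefore total fewer mg than an adult on the least intensive one.

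Long-term safety is a secondary objective and the stated purpose of Epoch 4. The section 1.3 groups are the columns for adverse events (SAP 1.13.1), laboratory data (1.13.3), vital signs (1.13.4) and the CRP, SAA and PGA summaries (1.10.5). The lowest column would mix patients on 150 mg q8w with low-weight patients on up to four times the matching mg/kg regimen. The top column would hold nobody who stayed at or below 40 kg. A reader comparing columns would take events in those children as low-exposure events.

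**Working it through.** **Inputs.** Epoch 4 runs from Day 281 to Day 785 (72 weeks). Counting rule from the Epoch 3 example in SAP 1.3: three q8w doses, 450 mg, "with no dose at day 281 (belongs to epoch 4". By the same rule the Day 281 dose counts in Epoch 4 and, as an assumption, no Day 785 dose is counted. Protocol 3.1.4 gives the q4w visits: "Patients up-titrated to q4w administration will come back every 4 weeks for unscheduled visits at Day 309", and eight more to Day 757, in addition to the 8-weekly visits.

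**Number of doses.** q8w: Days 281, 337, …, 729 = 9. q4w: 9 + 9 = 18.

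**The SAP's own cut-offs, reproduced.** Total = dose × number of doses.

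| Regimen | Fixed-dose total | mg/kg total (40 kg or less) |
|---|---|---|
| 150 mg or 2 mg/kg q8w | 9 × 150 = 1350 mg | 9 × 2 = 18 |
| 150 mg or 2 mg/kg q4w | 18 × 150 = 2700 mg | 18 × 2 = 36 |
| 300 mg or 4 mg/kg q8w | 9 × 300 = 2700 mg | 9 × 4 = 36 |
| 300 mg or 4 mg/kg q4w | 18 × 300 = 5400 mg | 18 × 4 = 72 |

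So 2700 and 5400 mg come out as full-course totals, and fixed-dose completers fall where the SAP describes.

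**Raw mg for completers of 40 kg or less** (mg/kg total × constant weight):

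| Weight | 36 mg/kg course | 72 mg/kg course |
|---|---|---|
| 10 kg | 360 mg | 720 mg |
| 20 kg | 720 mg | 1440 mg |
| 30 kg | 1080 mg | 2160 mg |
| 40 kg | 1440 mg | 2880 mg |

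- A 36 mg/kg course would need 2700/36 = 75 kg to leave the lowest group, so it never does at 40 kg or less.
- A 72 mg/kg course reaches 2700 mg only at 2700/72 = 37.5 kg. The top group would need 5400/72 = 75 kg.
- Below 1350/72 = 18.75 kg, a completed 4 mg/kg q4w course totals less than a completed 150 mg q8w course.
- Patients on 2 mg/kg q8w (18 mg/kg, at most 720 mg) are placed correctly.

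**Sensitivity to the Day 785 assumption.** With a Day 785 dose there are 19 q4w or 10 q8w doses. The maxima at 40 kg are 38 × 40 = 1520 mg (2 mg/kg q4w), 40 × 40 = 1600 mg (4 mg/kg q8w) and 76 × 40 = 3040 mg (4 mg/kg q4w). The 37.5 kg limit becomes 2700/76 = 35.5 kg. The conclusion does not change.

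**Comparison with Epoch 3.** Over 24 weeks, 4 mg/kg q4w gives 6 × 4 = 24 mg/kg. This exceeds 15, so the patient is in the top group. Protocol 3.1.4 has patients continue their last regimen and bars down-titration in Epoch 4. A 20 kg child who continues then totals 1440 mg and drops to the lowest group on unchanged dosing. A child on 2 mg/kg q4w moves from the middle group (6 × 2 = 12 mg/kg) to the lowest.

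**The case against.** The best defence is that these are descriptive, open-label displays and that other outputs show exposure properly. SAP 1.13.1 gives exposure-adjusted adverse event rates by the dose actually received. SAP 1.8 gives exposure summaries and a dose distribution through Epoch 4, and patient listings are provided. SAP 1.1 also promises separate safety reporting for patients under 2 years in Epoch 4. Dose increases follow flares, so dose is confounded with disease activity under any column scheme. All of this stands, and it limits what the columns could show. But the exposure-adjusted rates cover adverse events only, SAP 1.8 describes exposure rather than outcomes, and the separate reporting leaves out low-weight patients aged 2 years or more.

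A reader might go further and infer that the 2700 and 5400 mg cut-offs are themselves wrong, because they equal full-course totals and one missed dose drops a fixed-dose patient a group (17 × 150 = 2550, 8 × 300 = 2400 or 17 × 300 = 5100 mg). The documents do not support that. The groups are meant to hold starting regimens with or without flare. To keep a 150 mg q8w starter who later moves to q4w, the lowest group must run from 1350 up to 2700 mg. A single q8w-to-q4w switch leaves the described group only at Day 309 (18 × 150 = 2700 mg); at Day 365 the total is 17 × 150 = 2550 mg. Tripling the Epoch 3 cut-offs to 1800 and 3600 mg would instead move such patients up at seven of the nine switch visits (12 or more doses). Protocol 6.3 expects full compliance, since site staff give the injections.

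Nor do the documents support a return to the arms that Protocol section 9 introduces with "Treatment arms for the safety and efficacy analyses will include (taken into account their regimen in Epoch 3". SAP 1.3 gives a reason for leaving them: few patients are expected to be flare-free for 72 weeks. That list also has no arm for patients who go from 150 mg to 300 mg, which Protocol 3.1.4 allows.

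**Conclusion.** The concern holds for patients who stay at or below 40 kg, and it is a gap in the classification rule rather than a fault in the mg cut-offs. Completers of 2 mg/kg q4w or 4 mg/kg q8w always fall in the lowest Epoch 4 group. So do completers of 4 mg/kg q4w whose weight stays below 37.5 kg (35.5 kg if a Day 785 dose is counted). None can reach the top group. This contradicts the SAP's own Epoch 3 treatment of the same regimens.

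It would be too strong to infer that all children are misplaced: those above 40 kg receive fixed doses, and those on 2 mg/kg q8w are grouped correctly. It would also be too strong to infer that a trial conclusion is at risk, because neither the primary endpoint nor any hypothesis in the testing sequence uses these groups. The result assumes completed courses, a weight that stays within the stated range, and the SAP applied literally. The documents do not give the number of patients affected. The gap should be closed before the Epoch 4 tables are programmed.

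**What to change.** Keep 2700 and 5400 mg. Add to SAP 1.3 an Epoch 4 conversion for patients of 40 kg or less, built as in Epoch 3. With 150 mg = 2 mg/kg, the Epoch 3 cut-offs of 600 and 1200 mg equal 8 and 16 mg/kg, and the SAP sets its limits 1 mg/kg lower, at 7 and 15. The Epoch 4 cut-offs equal 36 and 72 mg/kg, so:

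- ≤35 mg/kg goes to <2700 mg
- >35 to ≤71 mg/kg goes to 2700 to <5400 mg
- >71 mg/kg goes to ≥5400 mg

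Completed courses of 18, 36, 36 and 72 mg/kg then fall in the same groups as their fixed-dose counterparts.

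The margin is thin: 1/72 = 1.4% at the top, against 1/16 = 6.25% in Epoch 3, and the SAP derives mg/kg from injected volume and weight at the visit. If volume rounding matters, sum nominal equivalents per dose instead (2 mg/kg counts as 150 mg, 4 mg/kg as 300 mg). This also handles patients who cross 40 kg during the epoch.

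The cost is SAP wording and table programming, with no new data. The columns would then show weight-equivalent rather than literal mg for these patients, which a footnote should say.

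Optional: early stopping lowers cumulative dose whatever the regimen. For example, a patient on 300 mg q4w who stops after 8 doses totals 2400 mg and is in the lowest group. A supplementary Epoch 4 adverse event and laboratory display by average dose per 4 weeks on treatment would address this. It needs a stated rule for time on treatment.
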